# 10.6 Missed Doses and Study Visits

Treatment will be interrupted because of Grade 3 or higher toxicity during any cycle beyond Cycle 1. Treatment may be resumed as described in Section 10.5.

Study visits that are missed because of clinic or subject unavailability (e.g., for reasons of public holiday, clinic closure, urgent personal matter, transportation problems), should be

made up when and if reasonably possible. For delayed doses, the dosing schedule should continue from the date of the delayed dose without omitting any doses of chemotherapy or any rest intervals between chemotherapy, if possible. Whenever possible, subsequent doses of chemotherapy should be advanced in time to synchronize with the actual date of administration of the delayed dose.

The relative timings of all other assessments and drug dosing may be moved to accommodate subject and clinic availability. Delays between sequential cycles in therapy, other than for reasons of toxicity, should not exceed 7 days, except as approved by the Sponsor medical monitor.

## 10.7 Stopping Rules

Stopping rules for this study are described in Section 8.1.3.

# 10.8 Packaging and Labeling

The Sponsor will supply the VX-984 as powder in high density polyethylene (HDPE) bottles with induction-sealed polypropylene caps. Study drug labeling will be in compliance with applicable local and national regulations. Additional details regarding packaging, labeling, and dispensing for VX-984 will be included in the Pharmacy Manual.

## 10.9 Study Drug Supply, Storage, and Handling

The Investigator, or an authorized designee (e.g., a licensed pharmacist), will ensure that all investigational product is stored in a secured area, under recommended storage conditions as outlined in the Pharmacy Manual, and in accordance with applicable regulatory requirements. To ensure adequate records, all study drugs will be accounted for as described in Section 10.10 or via the drug accountability forms as instructed by the Sponsor.

Drug supply will be sent to the site in the form of bulk bottles, with pharmacist or designated study staff allocating the necessary units to a subject-specific bottle. Empty bottles and caps will be provided by the sponsor. If a site needs to use a bottle other than those provided by the sponsor, the site should request prior approval from the sponsor. The site will apply a label to the bottles.

### 10.10 Drug Accountability

The pharmacist or designated study site staff will maintain information regarding the dates and amounts of (1) study drug received, (2) study drug dispensed to the subjects, and (3) study drug returned by the subjects. Subjects will be instructed to return all used and unused materials associated with the study drug to the site. These materials will be retained at the site according to instructions provided by the Sponsor or its designee until inventoried by the study monitor. The study monitor will review study drug records and inventory throughout the study.

# 10.11 Disposal, Return, or Retention of Unused Drug

The study site staff or pharmacy personnel will retain all materials returned by the subjects until the study monitor has performed drug accountability. At the end of the study, the study monitor will provide instructions as to the disposition of any unused investigational product. If the study monitor authorizes destruction at the study site, the Investigator will ensure that

the materials are destroyed in compliance with applicable environmental regulations, institutional policy, and any special instructions provided by the Sponsor. Destruction will be adequately documented.

# 10.12 Compliance

For study drug doses administered when on-site at the clinic, doses will be administered under the direct supervision of the Investigator or designee. A hand-and-mouth check will be done after each dose administration in the clinical research unit to ensure 100% study treatment compliance.

For study drug doses administered during the outpatient periods of the study, drug accountability will be assessed at each visit by counting returned dosage units. Discrepancies will be discussed with the subject and recorded in the source documents. If subjects demonstrate continued noncompliance of study drug dosing despite educational efforts, the Investigator will contact the medical monitor to discuss discontinuing the subject from the study.

# 10.13 Blinding and Unblinding

This will be an open-label study.

#### 11 ASSESSMENTS

## 11.1 Timing of Assessments

The timing of assessments is shown in Table 3-1, Table 3-2, and Table 3-3.

# 11.2 Subject and Disease Characteristics

Subject and disease characteristics include the following: demographics, medical history, height, weight, type of cancer (including histologic subtype), tumor stage at baseline, date of cancer diagnosis, prior chemotherapy and radiation therapy, date and duration of most recent cancer therapy, and WHO performance status at baseline.

#### 11.3 Pharmacokinetics

#### 11.3.1 Blood Sampling

For the evaluation of plasma concentrations of VX-984 and PLD, plasma samples will be collected according to the Schedule of Assessments (Table 3-2 and Table 3-3). These samples may also be used for evaluations of metabolites of VX-984, for further evaluation of the bioanalytical method, and for analyses that provide information on the metabolic pathways used by or affected by VX-984.

Actual sampling times may change upon agreement of the clinical pharmacologist and Investigator, but the number of samples will remain the same. All efforts will be made to obtain the PK samples at the exact nominal time relative to dosing. Acceptable windows for sampling times are shown in Table 11-1. Samples collected outside of these acceptable windows will be considered protocol deviations. The exact time of the sample collection will be noted.

**Table 11-1** Acceptable Pharmacokinetic Sampling Windows

Sampling Time	Time From Scheduled Sampling Allowed
Predose	- 120 minutes
From 0.5 up to $\leq$ 4 hours after study drug dosing	± 15 minutes
From $> 4$ up to $\le 72$ hours after study drug	± 120 minutes
dosing	

### 11.3.2 Urine Sampling

Urine will be collected for measurement of VX-984 PK in the Lead-in Period according to the Schedule of Assessments (Table 3-1).

[figure not shown]
Detailed instruction for urine PK sample collection, processing, handling, and storage will be provided in the Laboratory Manual.

### 11.3.3 Processing and Handling of Pharmacokinetic Samples

Detailed procedures for the collection of blood and urine samples and further procedures for processing and handling of samples for PK analysis will be provided in the Laboratory Manual. The shipment address and assay laboratory contact information will be provided to the investigational site before initiation of the study.

## 11.3.4 Bioanalysis

Samples will be analyzed using a validated analytical method in compliance with the Sponsor or designee standard operating procedures. A description of the assay and validation data will be provided in separate reports.

Subjects with measurable disease will be assessed by standard criteria (RECIST 1.1). Changes in the largest diameter (unidimensional measurement) of the tumor lesions and the shortest diameter in the case of malignant lymph nodes are used in the RECIST criteria. Refer to the RECIST 1.1 publication for additional information.

CT scans will be read locally for all parts of the study. The applicable overall response category for each visit that includes disease assessment, based on evaluation of CT scan by a qualified radiologist local to the Investigator, will be recorded in the electronic case report form (eCRF). Determination of subject study disposition (i.e., discontinuation or extension of therapy) will be based on the interpretation of disease progression from the local evaluation of the CT scan.

Information regarding anatomical imaging (CT scans) will be collected according to the Imaging Manual. The sponsor will engage an imaging contract research organization to facilitate acquisition and potential interpretation of images.

In addition to the standard RECIST 1.1 assessments, anatomical images collected may be analyzed using image analysis techniques that enable additional insights into tumor changes following treatment, including, but not limited to, assessments of 3D-tumor volumes and

tumor necrosis (for tumors amenable to volume and necrosis assessment). Additional information will be provided in the Imaging Manual. These additional imaging analyses will be exploratory in nature and will not be used to make subject treatment decisions or as a replacement of standard RECIST 1.1.

Historical CT scans may be collected and analyzed to enable assessment of historical and ontreatment tumor growth dynamics.

CT scans expose patients to medical radiation. The scans performed in this study should be considered within the standard of care for the subject. It is important that all scans performed on a subject should be consistent. This includes use of the same scanner, acquisition parameters, and administration of contrast agents (to the extent it is clinically feasible).

### 11.7 Safety

Safety evaluations will include AEs, clinical laboratory assessments, clinical evaluation of vital signs, ECGs, echocardiograms, and PEs.

#### 11.7.1 Adverse Events

All AEs will be assessed, documented, and reported in accordance with ICH GCP guidelines. Section 13.1 outlines the definitions, collection periods, criteria, and procedures for documenting, grading, and reporting AEs. A separate document that details AE CRF completion guidelines for Investigators as well as training will be provided.

# 11.7.2 Clinical Laboratory Assessments

Blood and urine samples will be analyzed at a local or central laboratory. At the Screening Visit, blood specimens will be collected for safety laboratory tests. Samples will be collected as specified in the Schedule of Assessments (Table 3-1, Table 3-2, and Table 3-3).

To facilitate timely administration of study drug, safety labs may be obtained up to 3 days before dosing. If labs are drawn before the day of dosing, they should be recorded as corresponding to the day of dosing.

Laboratory test results that are abnormal and considered clinically significant will be reported as AEs (see Section 13.1).

The safety laboratory test panels are shown in Table 11-2.

Serum Chemistry	Hematology	Urinalysis a
Glucose	Hemoglobin	Leukocyte esterase
Blood urea nitrogen b	Erythrocytes:	Nitrite
Creatinine	Mean corpuscular volume	Urobilinogen
Sodium	Platelets	Urine protein
Potassium	Reticulocytes (absolute) c	pН
Calcium	Leukocytes	Urine blood
Chloride	Differential (absolute and percent):	Specific gravity
Magnesium	Eosinophils	Urine ketones
Bicarbonate	Basophils	Urine bilirubin
Inorganic phosphate	Neutrophils	Urine glucose
Total bilirubin, direct bilirubin	Lymphocytes	
ALP	Monocytes	
AST	Coagulation c	
ALT	Activated partial thromboplastin time	
Total protein	Prothrombin time	
Albumin	Prothrombin time International	
Creatine kinase c	Normalized Ratio	
Uric acid c		

**Table 11-2** Safety Laboratory Test Panels

- b If blood urea nitrogen cannot be collected, urea may be substituted.
- c Creatine kinase, uric acid, and reticulocytes (absolute) parameters will be tested only at Screening and Safety Follow-up. Coagulation parameters will be tested only at Screening.

Additional tests at screening: The following additional tests will be performed during screening to assess eligibility:

- Serum beta-human chorionic gonadotropin (β-hCG) for all female subjects
- Serum FSH for suspected postmenopausal female subjects only. Levels will be within the laboratories range for postmenopausal for subjects to be considered of non-childbearing potential.

Clinical laboratory assessments from screening will have no clinically significant findings that preclude participation in the study, as judged by the Investigator, for a subject to receive study drug.

Pregnancy testing for female subjects of childbearing potential (as defined in Section 11.7.6.1):

- Subjects in Part A receiving VX-984 with Lead-in Period will have a urine β-hCG test on Day -14, Day 1 of VX-984 and PLD combination therapy, and every 4 weeks thereafter through the Safety Follow-up Visit
- Subjects in Part A receiving VX-984 without Lead-in Period and subjects in Part B will have a urine β-hCG test on Day 1 of VX-984 and PLD combination therapy, and every 4 weeks thereafter through the Safety Follow-up Visit.

<sup>a If urinalysis results are positive for leukocyte esterase, nitrite, protein, or blood, microscopic examination of urine will be performed and results for provided for leukocytes, erythrocytes, crystals, bacteria, and casts.

When there are no scheduled study visits, pregnancy testing will be performed using a urine home pregnancy test kit provided by the study site.

If a urine pregnancy test is positive, all study drug dosing will stop and the pregnancy will be confirmed with a serum  $\beta$ -hCG test. If confirmed, the pregnancy will be reported and the subject will be permanently withdrawn from study drug dosing as discussed in Section 11.7.6.2. If a pregnancy test is positive, the procedures outlined in Section 11.7.6.2 will be followed.

Additional Evaluations: Additional clinical laboratory evaluations will be performed at other times if judged to be clinically appropriate.

# 11.7.3 Physical Examinations and Vital Signs

A PE of all body systems and vital signs assessment will be performed at screening and select study visits (Table 3-1, Table 3-2, and Table 3-3). At other visits, symptom-directed PEs and symptom-directed vital sign assessments can be performed at the discretion of the Investigator.

A PE includes a review of the following systems: head/neck/thyroid; eyes/ears/nose/throat (EENT); respiratory; cardiovascular; lymph nodes; abdomen; skin; musculoskeletal; and neurological. Breast, anorectal, and genital examinations will be performed when medically indicated. After screening, any clinically significant abnormal findings in PEs will be reported as AEs.

Vital signs include blood pressure (systolic and diastolic), temperature, pulse rate, and respiration rate. These will be assessed following a 5-minute rest in the supine position.

# 11.7.4 Electrocardiograms

Standard 12-lead ECGs will be performed using a machine with printout according to the Schedule of Assessments (Table 3-1, Table 3-2, and Table 3-3). Additional standard 12-lead ECGs will be performed at any other time if clinically indicated. The performance of all ECGs will adhere to the following guidelines:

- The subject will be instructed to rest in the supine position for at least 5 minutes before having an ECG performed
- The ECG will be performed before any other procedures that may affect heart rate, such as blood draws.

The ECG traces will be manually read at the study site at the Screening and Safety Follow-up Visits. A printout of the ECG traces will be made for safety review by the Investigator and maintained with source documentation. Clinically significant ECG abnormalities occurring during the study through the Safety Follow-up Visit will be recorded as AEs.

# 11.7.5 Echocardiogram

Echocardiograms will be collected from all subjects according to the Schedule of Assessments (Table 3-1, Table 3-2, and Table 3-3).

# 11.7.6 Contraception and Pregnancy

# 11.7.6.1 Contraception

#### **Male Subjects:**

Acceptable contraceptive methods must be used from the Screening Visit through 6 months after the last dose of study drug, and include the following:

- True abstinence (absence of any sexual intercourse), when in line with the preferred and usual lifestyle of the subject. Periodic abstinence (e.g., calendar, ovulation, symptothermal, postovulation methods), and withdrawal are not acceptable methods of contraception
- Condom with spermicide and the female partner must use an acceptable method of contraception, such as an oral, transdermal, injectable, or implanted steroid-based contraceptive, or a diaphragm or cervical cap with spermicide
- Vasectomy (with a negative sperm postvasectomy semen analysis) at least 6 months before first dose of study drug and 1 additional acceptable contraception method.

Male subjects must not donate sperm from the Screening Visit through 6 months after the last dose of study drug.

- Note 1: Male condom cannot be used with female condom due to risk of tearing.
- Note 2: The use of birth-control methods does not apply if the female partner has a bilateral oophorectomy, hysterectomy, or is postmenopausal (as defined below).

### Female Subjects of Nonchildbearing Potential:

Female subjects of non-childbearing potential must meet at least 1 of the following criteria:

- Postmenopausal: Female subjects, less than 60 years of age, who have been amenorrheic for at least 2 years and have a serum FSH level within the laboratory's reference range for postmenopausal females. Female subjects who are 60 years of age or older and who have been amenorrheic for greater than 2 years will be assumed to be postmenopausal
- Documented hysterectomy or bilateral oophorectomy or both.

All other female subjects (including subjects with tubal ligations and subjects who do not have a documented hysterectomy) will be considered to be of childbearing potential.

#### Female Subjects of Childbearing Potential:

Acceptable nonhormonal, contraceptive methods must be used from the 28 days before first dose of study drug through 6 months after the last dose of study drug and include the following:

 True abstinence (absence of any sexual intercourse), when in line with the preferred and usual lifestyle of the subject. Periodic abstinence (e.g., calendar, ovulation, symptothermal, postovulation methods) and withdrawal are not acceptable methods of contraception

- Double barrier contraception such as diaphragm or cervical cap with spermicide and the male partner must use a condom with spermicide
- Intrauterine device (nonhormone-releasing) in place for at least 90 days previously and the male partner must use a condom with spermicide
- Bilateral tubal ligation at least 6 months previously and 1 additional acceptable contraception method
- Vasectomy of the male partner (with a negative sperm postvasectomy semen analysis) at least 6 months before first dose of study drug and 1 additional acceptable contraception.

#### 11.7.6.2 **Pregnancy**

Subjects will be counseled to inform the Investigator of any pregnancy that occurs during study treatment and for 90 days after the last dose of study drug(s).

If a subject or the female partner of a male subject becomes pregnant while participating in the study, study drug will be permanently discontinued immediately. The Investigator will notify the medical monitor and the Sponsor Global Patient Safety (GPS) within 24 hours of the site's knowledge of the subject's (or partner's) pregnancy using the Pregnancy Information Collection Form. The subject or partner will be followed until the end of the pregnancy and the infant will be followed for 1 year after the birth, provided informed consent is obtained. A separate ICF will be provided to explain these follow-up activities. Pregnancy itself does not constitute an AE.

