# 8.1.4 Follow-up (Parts A and B)

All subjects, regardless of reason for discontinuation, will have a Safety Follow-up Visit  $28 (\pm 7)$  days following the last dose of study drug, during which the procedures listed in Table 3-3 will be completed. In addition, all subjects who receive all scheduled study drug doses through Cycle 1, have not had evidence of disease progression, and have not initiated

cancer therapy outside of the study protocol will have radiologic follow-up 5 weeks  $(\pm 1 \text{ week})$  after the last cycle of chemotherapy.

A survival follow-up assessment will be performed for all subjects at the last subject last visit for that part. For the survival follow-up assessment, every subject who is not known to have died during the course of the study will be called to ascertain whether the subject is alive, if the subject has initiated another therapy, or if the subject died. If the subject has initiated another therapy or died, the date of initiation of the other therapy or date of death will be confirmed.

Subjects in Part B who complete at least 6 cycles of treatment, discontinue for reasons other than disease progression, and do not have disease progression on the radiologic follow-up visit will be followed by staging CT scan (if possible) approximately every 8 weeks until disease progression, the subject starts a new line of therapy, the subject dies, the study closes, or the subject is at least 12 months from end of treatment, whichever comes first.

Finally, for Part B, regardless of disease progression or initiation of new line of therapy, subjects may be followed by telephone, electronic, or mail communication, or in person, every 3 months for up to 1 year or until the subject is lost to follow-up or dies, whichever occurs first

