#### 9.2 Exclusion Criteria

Subjects who meet any of the following exclusion criteria will **not** be eligible.

- 1. Previous radiotherapy (unless brachytherapy), endocrine therapy, chemotherapy, or exposure to investigational medicinal products during the 4 weeks (6 weeks for nitrosoureas and Mitomycin-C) or 4 drug half-lives before the planned administration of the first dose of study drug, whichever is greater. Previous immunotherapy during the 4 weeks before the planned administration of the first dose of study drug
- 2. For Part B only:
  - Subjects with uterine carcinosarcoma
  - o Prior anthracycline therapy
  - o More than 1 prior chemotherapy regimen (a subject who received first-line carboplatin and taxane and then receives the same taxane second-line will be considered to have had 1 prior chemotherapy regimen)
- 3. Unresolved toxicity of CTCAE Grade 2 or greater from previous anti-cancer therapy or radiotherapy, excluding
  - Alopecia

- Anemia or leukopenia if absolute neutrophil counts fall within limits specified in Inclusion Criterion 6 and is not decreasing at the time of treatment
- Other toxicities that in the opinion of the Investigator and the sponsor should not exclude the subject
- 4. History of spinal cord compression or brain metastases, unless asymptomatic, treated, stable, and not requiring treatment with steroids for at least 4 weeks before the planned administration of the first dose of study drug. Any history of leptomeningeal metastases
- 5. Female subjects who are pregnant or lactating at Screening, or plan to become pregnant while on study or within 6 months after the last dose of study drug
- 6. Female subjects of childbearing potential must adhere to contraception guidelines as outlined in the protocol. Female subjects will be considered to be of nonchildbearing potential if they have undergone surgical hysterectomy or bilateral oophorectomy or have been amenorrheic for more than 2 years with a screening serum follicle-stimulating hormone (FSH) level within the laboratory's reference range for postmenopausal females
- 7. Male subjects with partners of childbearing potential must agree to adhere to contraception guidelines
- 8. Male subjects with pregnant or lactating partners or partners who plan to become pregnant while on study or within 6 months after the planned administration of the last dose of study drug

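### Subjects are told to report pregnancies for only 90 days after the last dose, while contraception and the planned-pregnancy exclusions run for 6 months

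*Protocol*

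**What the plan says.** Protocol Section 11.7.6.2 sets the reporting instruction: "Subjects will be counseled to inform the Investigator of any pregnancy that occurs during study treatment and for 90 days after the last dose". Once a site knows of a pregnancy in a subject or a male subject's partner, it must notify the medical monitor and the sponsor's safety group within 24 hours. The pregnancy is then followed to its end and, with consent, "the infant will be followed for 1 year after the birth". The section adds that pregnancy is not in itself an adverse event.

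The other reproductive provisions use a longer period:

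- Women of childbearing potential must use contraception "from the 28 days before first dose of study drug through 6 months after the last dose of study drug" (Section 11.7.6.1).
- For men, the same section says: "Acceptable contraceptive methods must be used from the Screening Visit through 6 months after the last dose of study drug". Its ban on sperm donation also ends at 6 months.
- Exclusion criterion 5 (Section 9.2) covers women who "plan to become pregnant while on study or within 6 months after the last dose of study drug".
- Exclusion criterion 8 covers men whose partners plan a pregnancy on study or "within 6 months after the planned administration of the last dose of study drug".

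Scheduled urine pregnancy tests continue "every 4 weeks thereafter through the Safety Follow-up Visit" (Section 11.7.2). Section 8.1.4 places that visit 28 (± 7) days after the last dose. It also plans a survival contact, in which each subject not known to have died "will be called to ascertain whether the subject is alive, if the subject has initiated another therapy, or if the subject died".

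**The concern.** By requiring contraception for 6 months, the protocol treats conception anywhere in that time as a risk to avoid. A pregnancy between day 91 and month 6 is therefore a contraception failure inside the sponsor's own risk period, which is the kind of event that pregnancy follow-up exists to capture. Yet the reporting instruction has lapsed by then.

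If the subject does not volunteer the information, notification, follow-up to the end of the pregnancy and the infant's first-year follow-up need not start. A drug-related birth defect would be reported only if the site happened to hear of it, and pregnancies with other outcomes could go unrecorded. Partners of male subjects are the more exposed group, because the protocol schedules no test for them at any time.

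The drug is a first-in-human inhibitor of DNA repair given with an anthracycline, so each exposed pregnancy would be scarce information. Nothing in the estimation of the MTD, the response analysis or the safety tables depends on this point.

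**Working it through.** The plan gives no figure of its own to reproduce. The check compares the periods, converts them to days, and then asks whether any other provision covers the difference.

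**Periods after the last dose**

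| Provision | Source | Ends |
|---|---|---|
| Instruction to report a pregnancy | Protocol 11.7.6.2 | 90 days |
| Contraception, women | Protocol 11.7.6.1 | 6 months |
| Contraception and sperm-donation ban, men | Protocol 11.7.6.1 | 6 months |
| Planned pregnancy, women | Protocol 9.2, criterion 5 | 6 months |
| Planned pregnancy, partners of men | Protocol 9.2, criterion 8 | 6 months (from the planned last dose) |
| Scheduled pregnancy tests | Protocol 11.7.2 and 8.1.4 | day 28 ± 7 |

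The 90-day figure differs from all five 6-month provisions, and the documents give no reason for it.

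**Conversion to days.** SAP Section 9 takes 1 month as 30.4375 days.

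- 6 months = 6 × 30.4375 = 182.6 days
- Days without an instruction to report = 182.6 − 90 = 92.6 days
- Share of the contraception period not covered = 92.6 / 182.6 = 50.7%; share covered = 90 / 182.6 = 49.3%

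**Testing.** The last scheduled test falls between day 28 − 7 = 21 and day 28 + 7 = 35. Of the full 182.6 days, between 182.6 − 35 = 147.6 and 182.6 − 21 = 161.6 days have no scheduled test. All 92.6 days of the reporting gap lie inside that untested stretch.

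**Does anything else prompt a report after day 90?**

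- Routine adverse event collection ends at the Safety Follow-up Visit, or 28 days after the last dose if that visit does not take place (Protocol 13.1.1.3). Pregnancy is not an adverse event in any case.
- The radiologic follow-up comes at 5 (± 1) weeks. Counted from the last dose, as in the synopsis, that is day 42 at the latest (6 × 7).
- The survival contact covers vital status and new therapy only.
- The optional contact every 3 months applies to Part B only and does not mention pregnancy (Protocol 8.1.4). SAP Section 7 says that Part B is not being pursued.
- The long-term follow-up listing in SAP Section 10.1 has no pregnancy item.
- Serious adverse events after the Safety Follow-up Visit stay reportable if related to study drug (Protocol 13.1.2.2), and a birth defect is serious by definition (13.1.2.1). This covers one outcome of a pregnancy, not the pregnancy itself.

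After the Safety Follow-up Visit, the subject's own report is the only planned route by which the site would learn of a pregnancy. The instruction to make that report stops at day 90.

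**The case against.** The strongest reply is that there is no contradiction. Preventing pregnancy and recording it are separate obligations, and nothing in the documents requires them to last equally long. That stands: the 90 days is a design choice, and aligning it is a recommendation. It does not explain why capture should stop halfway through a period in which the protocol still forbids conception.

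Second, safeguards remain. Related birth defects are reportable without a time limit, the investigator's 24-hour duty carries no 90-day limit, and some later contacts give a site a chance to hear of a pregnancy. All of this is true, but each safeguard depends on the site finding out. No later contact is stated to ask, and the 24-hour clock starts only when the site knows.

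Third, the consent pages were not available, and Section 11.7.6.2 mentions a separate consent form for pregnancy follow-up that was not seen either. Subjects may already be told 6 months. This limits the finding to the available text. Even so, the protocol's own instruction to sites says 90 days.

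Fourth, the practical effect is very small. Postmenopausal women and those with a documented hysterectomy or oophorectomy are not of childbearing potential. Part A is small and enrols patients with advanced cancer. This is accepted, and it is why the point ranks as a minor improvement.

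Finally, the follow-up paragraph refers to pregnancies that arise during study participation, which could be read as excluding one at month 5. That phrase introduces the rule on stopping study drug and already sits beside a reporting period that extends past the last dose, so it does not defeat the change.

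**Conclusion.** The concern holds, as a minor point of safety capture. In the available text, about 92.6 of 182.6 days (51%) of the post-dose contraception period carry no instruction to report a pregnancy, and no other planned procedure fills that time.

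The size rests on the SAP's month length and is a share of days. The documents give no pregnancy rate, so no expected count can be stated. It should be low, given about 50 planned Part A subjects with advanced cancer and contraception still required throughout the gap. The conclusion also assumes that the unseen consent material does not already set a longer reporting period.

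**What to change.** In Protocol Section 11.7.6.2, replace 90 days with 6 months, so that the reporting instruction matches Section 11.7.6.1 and exclusion criteria 5 and 8. Make the same change in the subject counselling or consent text if it repeats the 90-day figure. Do not remove the mismatch by shortening contraception.

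The cost is one figure in the protocol and possibly one in subject-facing text. Under Section 13.2.3 it is still a protocol modification: it needs investigator and sponsor approval and submission to the regulatory authorities, so it is best carried with another amendment if one is due. It adds no visits, tests or analyses, and the SAP needs no change.
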